12.5.2 Safety endpoints

For all safety analyses, the Safety set will be used.

Safety summaries (tables, figures) include only data from the on-treatment period with the exception of baseline data which will also be summarized where appropriate (e.g. change from baseline summaries). In addition, a separate listing of death including on treatment and post treatment deaths will be provided. In particular, summary tables for adverse events (AEs) will summarize only on-treatment events, with a start date during the on-treatment period (treatment-emergent AEs).

Adverse events

All information obtained on adverse events will be displayed by participant.

The number (and percentage) of participants with treatment emergent adverse events (events started after the first dose of study medication or events present prior to start of treatment but increased in severity based on preferred term) will be summarized in the following ways:

- by primary system organ class and preferred term.
- by primary system organ class, preferred term and maximum severity.
- by preferred term.

Separate summaries will be provided for study medication related adverse events, serious adverse events, other significant adverse events leading to discontinuation.

A participant with multiple adverse events within a primary system organ class is only counted once towards the total of the primary system organ class.

[REDACTED]

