			13. Removed analysis using the per-protocol set	16. Section 2.6.2 Statistical hypothesis, model, and method of analysis
			14. Removed analysis of percent change from baseline and Month 6 re-baseline in lesion volume parameters	17. Section 2.7.1 Adverse events (AEs)
			15. Clarified determination of number of new/enlarging T2 lesions for derivation of annualized new/enlarging T2 lesion rate	18. Section 2.7.1 Adverse events (AEs)
			16. Removed observed case approach for summarization of participants with confirmed relapses	19. Section 2.7.1.1 Adverse events of special interest / grouping of AEs
			17. Added summaries for treatment-related SAEs and AEs occurring with frequency >5%	20. Section 2.10 Patient-reported outcomes
			18. Added details regarding summarization of AEs needed for ClinicalTrials.gov and EudraCT	21. [REDACTED]
			19. Removed summary of infection-related AEs	22. [REDACTED]
			20. Clarified that only total raw score for NeuroQOL Communication short form domain will be summarized	23. [REDACTED]
			21. Indicated that analysis of NfL values will not occur for the Month 18 interim analysis; NfL values will be analyzed at the time of the final analysis for the study	24. [REDACTED]
			22. [REDACTED]	25. Section 4 Change to protocol specified analyses
				26. Section 5.1.3.3 Other imputations
				27. Section 5.1.3.4 Data handling for relapses within 30 days of onset of previous relapses or relapses with duration beyond 90 days
				28. Section 5.3 Laboratory parameters derivations
				29. Section 5.5 Rule of exclusion criteria of analysis sets
				30. Section 6 Reference

---

Date	Time point	Reason for update	Outcome for update	Section and title impacted (Current)
			23. Removed analysis of [REDACTED] adverse events over the course of the study	
			24. Updated derivations for PDC and MPR	
			25. Indicted removal of analysis of [REDACTED] adverse events over the course of the study	
			26. Clarified MS history date imputation rules	
			27. Removed severity determination of "linked" relapses	
			28. Added rules for conversion of character to numeric continuous laboratory values	
			29. Removed reference to per-protocol set	
			30. Added Brookmeyer and Crowley reference	

---

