**Table 2 Month 18 interim analysis data cut-off for different participant scenarios**

Participant scenario	Cut-off	Participant data included in Month 18 interim analysis (primary analysis)
Completed Month 18 visit	Date of Month 18 visit + 7 days (inclusive)	All available data up to the date of the Month 18 visit + 7 days (inclusive)*
Did not complete Month 18 visit		
Discontinued study prior to Month 18 visit	None	All available data
Did not discontinue study prior to Month 18 visit	Date of next scheduled visit after Month 18 (exclusive)	All available data up to the date of the next scheduled visit (including home visit) after Month 18 (exclusive).** If the next scheduled visit after Month 18 has not been completed, all available data is used.

\* Including data such as adverse events, medications, non-drug therapies/procedures, protocol deviations and relapses that started prior to or on the date of the Month 18 visit + 7 days.

\*\* Including data such as adverse events, medications, non-drug therapies/procedures, protocol deviations and relapses that started prior to the date of the next scheduled visit (including home visit) after Month 18.

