### **2.7.1 Adverse events (AEs)**

Adverse events (AEs) will be coded using MedDRA terminology. The MedDRA version used for reporting the study will be indicated in a footnote on relevant outputs.

For reporting purposes, summary tables for AEs will summarize only the following events for ofatumumab-treated participants and healthy control participants:

- On-treatment events (treatment-emergent AEs), which started or worsened on or after the date of the first dose of ofatumumab for ofatumumab-treated participants
- On-study events, which started or worsened on or after the date of the date of Week 0 visit for healthy control participants

The number and percentage of participants with treatment-emergent/on-study AEs will be summarized for the open-label treatment phase, open-label extension period and overall, in the following ways using the SAF or HCAS, as appropriate:

- by Cohort, primary SOC and PT
- by Cohort, primary SOC, PT and maximum severity
- by Cohort and PT

Separate summaries will be provided using the SAF or HCAS, as appropriate, for treatment-emergent/on-study AEs occurring with a frequency of >5% in either Cohort, treatment-related AEs (only applicable to ofatumumab-treated participants), AEs leading to study drug interruptions (only applicable to ofatumumab-treated participants), serious adverse events (SAEs), treatment-related SAEs (only applicable to ofatumumab-treated participants) and other significant AEs leading to discontinuation.

In addition, an overview of treatment-emergent/on-study AEs will be summarized for the open-label treatment phase, open-label extension period and overall, presenting the number and percentage of participants having at least one AE for each of the categories described above.

If a participant reported more than one AE with the same PT, the AE with the greatest severity will be presented. A participant with multiple AEs within a primary SOC is only counted once towards the total of the primary SOC.

Partial AE start and end dates will be imputed as outlined in [Section 5.1.2](#).

For the legal requirements of ClinicalTrials.gov and EudraCT, two required tables on on-treatment/treatment-emergent AEs which are not SAEs with an incidence greater than 5% and

on on-treatment/treatment-emergent SAEs and SAEs suspected to be related to study treatment will be provided by SOC and PT on the SAF.

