If for a same patient, several consecutive AEs (irrespective of study treatment causality, seriousness and severity) occurred with the same SOC and PT:

- A single occurrence will be counted if there is  $\leq 1$  day gap between the end date of the preceding AE and the start date of the consecutive AE
- More than one occurrence will be counted if there is  $> 1$  day gap between the end date of the preceding AE and the start date of the consecutive AE

For occurrence, the presence of at least one SAE/SAE suspected to be related to study treatment/non-SAE has to be checked in a block e.g., among AEs in a  $\leq 1$  day gap block, if at least one SAE is occurring, then one occurrence is calculated for that SAE.

The number of deaths resulting from SAEs suspected to be related to study treatment and SAEs irrespective of study treatment relationship will be provided by SOC and PT.

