### **2.7.1.1 Adverse events of special interest / grouping of AEs**

The number and percentage of participants with at least one treatment-emergent AE in each of the following categories will be presented for the open-label treatment phase, open-label extension period and overall using the SAF:

- Injection site reaction
- Injection systemic reaction

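### Infections are compared with healthy controls only as participants with at least one event; an episode count and a person-time rate by Cohort would be a cheap addition

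*SAP*

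**What the plan says.** The Secondary Objectives row of the protocol summary includes comparison with healthy controls on adverse events. Protocol 1.2 and 4.1 name infections as an example of a safety outcome that control data can inform. Protocol 12.5.2 plans "The number (and percentage) of participants with treatment emergent adverse events", by SOC and PT, by maximum severity, and by PT.

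SAP 2.7.1 follows this and adds the control cohort: "The number and percentage of participants with treatment-emergent/on-study AEs will be summarized for the open-label treatment phase, open-label extension period and overall". Serious events get a separate by-Cohort summary. The counting unit is always the participant. Within a SOC, "A participant with multiple AEs within a primary SOC is only counted once towards the total of the primary SOC"; within a PT only the most severe event is shown; the overview table uses participants with at least one event.

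Occurrences are counted in one visible place, the tables for the public registries. The second of these is "on on-treatment/treatment-emergent SAEs and SAEs suspected to be related to study treatment will be provided by SOC and PT on the SAF". The rule merges events no more than one day apart when "several consecutive AEs (irrespective of study treatment causality, seriousness and severity) occurred with the same SOC and PT". Under SAP 2.2 the safety set equals the full analysis set, meaning participants who received study drug, so controls are not in these tables.

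SAP 2.7.1.1 says "The number and percentage of participants with at least one treatment-emergent AE in each of the following categories will be presented", but the categories are the two kinds of injection reaction, on the safety set. The document history for Amendment 2 records "Removed summary of infection-related AEs".

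**The concern.** Infection can recur. Once most participants have had one infection, the any-or-none percentage moves little when one cohort has more infections per person. It also depends on how long people were observed: a cohort with more early leavers shows a lower percentage at the same underlying rate. The ofatumumab and control groups are not randomised and may well leave at different rates; the plan states a dropout assumption for ofatumumab only.

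At stake is how well the trial describes one of the comparisons for which the control group was recruited. The data needed are already collected: protocol 16.1.2 requires all infections to be recorded as adverse events, and SAP 2.4.1 already summarises follow-up duration by Cohort without using it as a denominator for adverse events.

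**Working it through.** **Figures from the plan.** 118 ofatumumab participants, 50 controls, 18 months (1.5 years), 15% dropout for ofatumumab (SAP 3.1 and 3.2). The plan's own numbers reproduce: 1.96 × √(0.80 × 0.20/100) = 7.84%; 1.96 × √(0.85 × 0.15/100) = 7.00%; 100/0.85 = 117.6, so 118. There is no plan figure for infections.

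**Assumptions.** Control rate r of 0.2 to 2.0 infections per year; ofatumumab rate 1.5r; leavers depart uniformly over 18 months; 15% dropout in both cohorts unless stated. Counts are Poisson, or negative binomial with between-person (frailty) variance 0.5.

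**1. How the percentage behaves.** For a dropout share d and T = 1.5, the Poisson form is

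P(any) = (1 − d)(1 − e^(−rT)) + d[1 − (1 − e^(−rT))/(rT)].

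At r = 1.0, controls: 0.85 × 0.777 + 0.15 × (1 − 0.777/1.5) = 0.733. Ofatumumab at 1.5: 0.85 × 0.895 + 0.15 × (1 − 0.895/2.25) = 0.851. Over the range:

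| Control rate per year | Any infection, ofatumumab v control, Poisson | Same, frailty 0.5 | Gap (points) |
|---|---|---|---|
| 0.2 | 34% v 24% | 31% v 23% | 8-10 |
| 0.5 | 63% v 49% | 56% v 44% | 12-14 |
| 1.0 | 85% v 73% | 74% v 64% | 10-12 |
| 1.5 | 93% v 85% | 83% v 74% | 8-9 |
| 2.0 | 96% v 91% | 87% v 80% | 5-7 |

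The rate ratio is 1.5 in every row, yet the gap shrinks once infections are common.

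**2. Same percentage, different burden.** With full follow-up, 75% with any infection fits −ln(0.25)/1.5 = 0.92 per year with no between-person variation, or (0.25^(−φ) − 1)/(1.5φ) = 1.33 and 2.00 per year for frailty variance φ = 0.5 and 1.0.

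**3. Unequal follow-up.** Keep r = 1.0, ratio 1.5 and 15% dropout on ofatumumab, and vary control dropout:

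| Control dropout | Any, Poisson | Any, frailty 0.5 | Control participant-years |
|---|---|---|---|
| 0% | 85 v 78, gap 7 | 74 v 67, gap 7 | 50 × 1.5 = 75 |
| 30% | 85 v 69, gap 16 | 74 v 60, gap 14 | 50 × (0.70 × 1.5 + 0.30 × 0.75) = 64 |

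The expected rates stay at 1.5 and 1.0 per participant-year. At 15% dropout in both cohorts, participant-years are 118 × (0.85 × 1.5 + 0.15 × 0.75) = 164 and 50 × 1.3875 = 69, with about 246 and 69 expected episodes.

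Percentages with 2 or more infections do not escape the problem. Over the same change in control dropout their gap moves from 16 to 24 points (Poisson) or from 11 to 17 (frailty 0.5). Only the person-time rate is stable.

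**4. Matching numerator and denominator.** For someone who misses Month 18 but stays in the study, Table 2 of the SAP stops event data before the next scheduled visit: "Including data such as adverse events, medications, non-drug therapies/procedures, protocol deviations and relapses that started prior to the date of the next scheduled visit". If that is Month 21 (day 630), events run to day 629. The open-label phase duration in SAP 2.4.1 instead runs to last contact or end of study, possibly day 900: 900/629 = 1.43 times too long. With k such participants and 547 days (540 + 7) for the rest, the inflation of ofatumumab participant-years is

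[(118 − k) × 547 + 900k] / [(118 − k) × 547 + 629k],

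or 1.013 for k = 3 and 1.050 for k = 12 (k is assumed). With an end at day 720 it is 1.004 to 1.017.

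**5. Choice of episode rule.** Extending the one-day-gap rule across the whole SOC would avoid counting one illness twice, but makes the count depend on end dates. SAP 5.1.2 leaves a stop date missing when the year is missing and imputes December when the month is missing, so one open-ended infection could absorb all later ones. Simulated with a mean illness of 10 days, SOC-wide merging removes about 3% of episodes at 1.0 per year. That becomes about 6-10% if 5-10% of infections are open-ended (assumed). At 1.5 per year it goes from about 4% to 9-14%. At SOC/PT level the opposite error applies: if 10% of illnesses carry two PTs (assumed), episodes are over-counted by 10%.

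**The case against.** The strongest reply is that the plan contains no defect. SAP 2.7.1 gives the participant counts that protocol 12.5.2 specifies and adds controls, severity and serious events. That stands, and it is why this is an improvement only. The further argument that no objective calls for the comparison does not stand, given the wording of the protocol summary.

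A reader might infer that repeat infections vanish altogether. They do not. Two infections with different PTs appear in two PT rows, and SAP 2.1 has all data listed. Only same-PT repeats are lost from the tables. Listings would allow a later rate, but would not fix the episode rule and denominator in advance.

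A reader might also infer that the sponsor withdrew the infection comparison in Amendment 2. The log describes superseded text and shows neither the content nor the reason. Infections are still compared through the general SOC and PT tables.

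Unequal reporting is a fair objection and remains. Ofatumumab participants are told to contact the site about adverse events before home injections (protocol 6.3.2). Remote contacts are timed around self-injection (Table 8-1, footnote 6), and investigators are to remind participants of infection risk (16.1.2). With no true difference, 20% more reporting would show a rate 1.2 times control, and 50% more could not be told from a true ratio of 1.5. The existing percentages share this weakness, and a footnote does not remove it.

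**Conclusion.** The point holds as a low-priority improvement. In the visible SAP text, infections are compared by Cohort only as participants with at least one event per SOC or PT. Same-PT repeats are not shown, and nothing allows for different follow-up. Under assumed inputs (1.0 infection per year in controls, ratio 1.5, 18 months), control dropout of 0% rather than 30% changes the any-infection gap by about 7 to 9 points with no change in the rate ratio.

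The gain rests on infections being fairly common or follow-up being unequal, and the documents give no figure for either. At 0.2 per year with similar follow-up the existing percentage is enough. The documents do not support calling this a departure from the protocol. Nor do they support saying that percentages with 2 or more or 3 or more infections would cure the follow-up problem. Confidence is medium, because redacted parts of the SAP and the table shells might contain a relevant summary. The log also mentions removal of another adverse event analysis whose type is blacked out.

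**What to change.** Add to SAP 2.7.1.1 one descriptive table by Cohort (safety set and healthy control set) for the SOC Infections and infestations in the open-label treatment phase, giving number of episodes, participant-years and episodes per participant-year.

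- Count episodes with the existing one-day-gap rule at SOC/PT level. State that an infection with a missing or imputed end date does not absorb later infections.
- End each participant's time at the Table 2 adverse event cut-off, not at last contact or end of study.
- Percentages with 2 or more and 3 or more infections are optional, with the same follow-up caveat as the existing percentages.
- Keep all existing tables. Give no test and no rate ratio.
- Footnote that the contrast is non-randomised and open-label and that ofatumumab participants are prompted more to report infections.

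The cost is a little programming, including a person-time variable that differs from the duration in SAP 2.4.1; no new data are needed. The downsides are sensitivity to unequal reporting, some double counting of illnesses coded to two PTs, and little return if infections turn out to be rare.

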### **2.7.1.1 Adverse events of special interest / grouping of AEs**

The number and percentage of participants with at least one treatment-emergent AE in each of the following categories will be presented for the open-label treatment phase, open-label extension period and overall using the SAF:

- Injection site reaction
- Injection systemic reaction

### **2.7.2 Deaths**

All deaths, including on-treatment and post-treatment deaths for ofatumumab-treated participants, will be listed.

### **2.7.3 Laboratory data**

Shift tables using the low/normal/high/ (low and high) classification will be used to compare baseline to the worst on-treatment value for hematology and chemistry parameters using the SAF. In particular, the number and percentage of participants with laboratory values will be presented by low/normal/high/ (low and high) classifications to compare baseline to worst on-treatment value for the open-label treatment phase, open-label extension period and overall. Unscheduled assessments will be considered.

Values and changes from baseline in hematology and chemistry parameters will be summarized by time point with descriptive statistics using the SAF.

Laboratory abnormalities will be flagged in listings.

### **2.7.4 Other safety data**

#### **2.7.4.1 Vital signs**

Values and changes from baseline in the following vital signs will be summarized by Cohort and time point with descriptive statistics using the SAF or HCAS, as appropriate:

- Sitting systolic blood pressure (mmHg), sitting diastolic blood pressure (mmHg), pulse rate (beats per minute) and body temperature (°C)

#### **2.7.4.2 Smoking status**

The number and percentage of participants in each smoking status category (Former, Current, Never) will be presented by Cohort, time point and type of substance (Tobacco, Marijuana, Vape, Other substance) using the SAF or HCAS, as appropriate. In addition, at each time point the number and percentage of participants who are former or current smokers of any type of substance will be presented separately by Cohort using the SAF or HCAS, as appropriate

#### **2.7.4.3 Columbia-Suicide Severity Rating Scale (C-SSRS)**

The C-SSRS is a questionnaire that prospectively assesses suicidal ideation and suicidal behavior. The number and percentage of participants in the following categories will be presented by analysis period/study phase (all prior history, recent history, open-label treatment phase, open-label extension period and overall) using the SAF.

- Each of the 10 individual suicidal ideation and behavior categories (during the analysis period/study phase of interest)
- Any suicidal ideation (answer of ‘yes’ to at least 1 of the 5 suicidal ideation questions during the analysis period/study phase of interest)
- Any suicidal behavior (answer of ‘yes’ to at least 1 of the 5 suicidal behavior questions during the analysis period/study phase of interest)
- Any suicidal ideation or behavior (answer of ‘yes’ to at least 1 of the 10 suicidal ideation and behavior questions during the analysis period/study phase of interest)
- Non-suicidal self-injurious behavior (during the analysis period/study phase of interest)

The analysis period ‘All prior history’ includes data from the Lifetime assessment obtained at Screening or Baseline/Week 0. The analysis period ‘Recent history’ includes data from the Past 6 Months assessment obtained at Screening or Baseline/Week 0. If there are multiple assessments within an analysis period/study phase, results will be derived as the worst-case value (i.e., an answer of ‘yes’ for the category) for that analysis period/study phase.

In addition, the number and percentage of participants with the following post-baseline events will be presented ([Nilsson et al., 2013](#)) by study phase (open-label treatment phase and open-label extension period) using the SAF. Note: In these definitions, a category of 0 is assigned to a participant without suicidal ideation (i.e., a ‘no’ answer to all suicidal ideation categories).

- Worsening suicidal ideation compared to recent history: An increase in the maximum suicidal ideation category at any time post-baseline from the maximum suicidal ideation category during pre-treatment recent history.
- Worsening serious suicidal ideation compared to recent history: An increase in the maximum suicidal ideation category to 4 or 5 at any time post-baseline from not having serious suicidal ideation (categories of 0-3) during pre-treatment recent history.
- Emergence of serious suicidal ideation compared to recent history: A maximum suicidal ideation category of 4 or 5 at any time post-baseline from no suicidal ideation (category 0) during pre-treatment recent history.

- Improvement in suicidal ideation at last on-treatment measurement compared to recent history: A decrease in suicidal ideation score at last on-treatment measurement from pre-treatment recent history.
- Emergence of suicidal behavior compared to all prior history: The occurrence of suicidal behavior (categories 6-10) at any time post-baseline from not having suicidal behavior (categories 6-10) prior to treatment (includes “lifetime” and any other assessments prior to treatment taken prior to treatment).

A participant can only be counted once within a given category; however, a participant can be counted in more than one category. Suicidal ideation and behavior data will be listed. Detailed answers to C-SSRS items will be listed separately for participants with any suicidal ideation at any time post-baseline (i.e., a ‘yes’ answer to at least one of the five suicidal ideation questions at any time post-baseline) and for participants with any suicidal behavior at any time post-baseline (i.e., a ‘yes’ answer to at least one of the five suicidal behavior questions at any time post-baseline). Additional details are provided in the TFL Shells document.

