## 2.2 Analysis sets

The Full Analysis Set (FAS) will include all enrolled participants that received any study drug.

The Safety Analysis Set (SAF) will be the same as the FAS.

The Healthy Control Analysis Set (HCAS) will include all enrolled healthy control participants. This analysis set will be used in the analysis of data collected from healthy control participants.

The modified FAS (mFAS) will include all participants in the FAS except for those who discontinued treatment prematurely prior to Month 18 for reasons other than lack of efficacy or death, or those who completed their Month 18 visit but missed relapse/EDSS/MRI (Gd+ or

new/enlarging T2 lesions) at Month 6, 12 or 18, unless they showed disease activity (i.e., MRI activity after Month 6 through 18 or relapse/3-month clinical disability progression between Months 6 and 18). The mFAS will be used for NEDA-3, NEDA clinical and NEDA radiological efficacy analyses.

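### SAP 2.7.4.3 gives the C-SSRS improvement percentage on the whole safety set with no at-risk denominator, so it cannot exceed the pre-treatment prevalence of ideation

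*SAP*

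**What the plan says.** In the second part of SAP 2.7.4.3, "the number and percentage of participants with the following post-baseline events will be presented", and this is done "by study phase (open-label treatment phase and open-label extension period) using the SAF". On the sets, SAP 2.2 says "The Safety Analysis Set (SAF) will be the same as the FAS" and "The Full Analysis Set (FAS) will include all enrolled participants that received any study drug". Membership therefore depends on dosing alone, not on any C-SSRS state or on having a rating.

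The event definitions in 2.7.4.3 do depend on the pre-treatment state:

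- Scoring: "a category of 0 is assigned to a participant without suicidal ideation".
- Improvement, listed as "Improvement in suicidal ideation at last on-treatment measurement compared to recent history", is defined as "A decrease in suicidal ideation score at last on-treatment measurement from pre-treatment recent history".
- Emergence of serious ideation: "A maximum suicidal ideation category of 4 or 5 at any time post-baseline from no suicidal ideation (category 0) during pre-treatment recent history".
- Worsening to serious ideation starts from categories 0-3.
- Any worsening is a rise in the maximum category, so it must start below 5.
- Emergence of behavior starts from no behavior (categories 6-10) before treatment.

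The section gives no denominator other than the SAF. It cites a C-SSRS scoring guide for these events and leaves further detail to the TFL Shells.

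**The concern.** A percentage is easy to read when everyone in the denominator could have had the event. Here some participants cannot. Someone with no ideation in the six months before treatment sits at category 0 and has nothing to decrease. Counted in the SAF, that person looks like someone who could have improved and did not. The improvement figure then mixes two things: how many had ideation at entry, and how many of those got better. If ideation at entry is uncommon, the first dominates.

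The same mismatch affects the emergence and worsening rows, but there the people who cannot have the event are the ones who already had ideation or behavior, presumably a minority. Protocol 5.2 lists no exclusion for past suicidality, so mixed starting states are possible.

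Participants with no C-SSRS rating in the phase are a second group. This matters most for the extension, which is optional. After Month 18, Protocol Table 8-1 schedules the C-SSRS only at Month 30/EOS. Read literally, treated participants who never entered the extension would count there as event-free.

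**Working it through.** **Inputs**

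- Planned ofatumumab participants: 118 (Protocol 12.8.1; SAP 3.1). Used here as the approximate size of the SAF.
- Check on that figure: 100 evaluable with 15% dropout gives 100 / (1 - 0.15) = 117.6, rounded up to 118. It reproduces.
- Pre-treatment prevalence of ideation: not in the documents. Assumed 5%, 10% and 20%, that is 6, 12 and 24 of 118, with 2% and 30% (2 and 35 of 118) as outer cases.
- C-SSRS event rates: the documents give none, so there is no planned C-SSRS figure to reproduce.

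**Improvement.** Let N be the SAF, k the number with a recent-history category of 1 or more, and x the number who improve. Then

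SAF percentage = x/N = (k/N) × (x/k), and since x ≤ k, x/N ≤ k/N.

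This is algebra and holds at any prevalence. Only the sizes below rest on the assumption.

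| Assumed prevalence | k | Ceiling on the SAF (all k improve) | Same result among those with ideation |
|---|---|---|---|
| 5% | 6 | 6/118 = 5.1% | 6/6 = 100% |
| 10% | 12 | 12/118 = 10.2% | 12/12 = 100% |
| 20% | 24 | 24/118 = 20.3% | 24/24 = 100% |

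At the outer cases the ceiling is 2/118 = 1.7% and 35/118 = 29.7%. Prevalence alone therefore moves the best possible result from 1.7% to 29.7%.

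**Emergence of serious ideation.** At risk are those at category 0, that is N - k. For two events:

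| k | SAF | At risk | Ratio N/(N - k) |
|---|---|---|---|
| 6 | 2/118 = 1.7% | 2/112 = 1.8% | 1.05 |
| 12 | 2/118 = 1.7% | 2/106 = 1.9% | 1.11 |
| 24 | 2/118 = 1.7% | 2/94 = 2.1% | 1.26 |

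At k = 35 the at-risk figure is 2/83 = 2.4%. The other two ideation rows shift by no more than this at the same prevalence, because they exclude only part of the k: those at 4 or 5 for worsening to serious ideation, and those at 5 for any worsening. For emergence of behavior the shift depends on how many had prior behavior, which the documents do not give.

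**Precision of the at-risk figure.** If 3 of 6 improve, the SAF figure is 3/118 = 2.5% and the at-risk figure is 50%, with an exact 95% confidence interval of about 12% to 88%.

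**Missing ratings.** SAP 2.1.1 summarizes change from baseline only for participants with both values. Applied here, that rule would remove unrated participants, but it does not restrict by starting state. The documents give no basis for putting a number on missing ratings.

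**The case against.** The strongest reply is that the divisor is inferred. The SAP names the SAF but does not write out that every member is in the denominator. Row denominators often sit in table shells, and neither the TFL Shells nor the cited guide is available here. That stands as a caveat. However, where this SAP narrows a denominator elsewhere, it says so: SAP 2.6.2 does this for the T2 lesion rate and for the completer analysis of disability worsening. Section 2.7.4.3 has no such sentence.

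Three stronger readings are tempting, and the documents do not support them:

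- *The improvement row cannot be interpreted.* The number is shown with the percentage. The same section tabulates any ideation in recent history, and each behavior category in all prior history, on the same set. A reader can rebuild most of the at-risk denominator. What is missing is the restriction to those rated in the phase.
- *The safety percentages are always biased low.* Events per treated participant is a legitimate descriptive quantity, and SAP 2.7.1 uses it for adverse events. It equals the at-risk figure when everyone is at risk and rated, and otherwise lies below it, by little in the emergence examples above.
- *There is a true improvement rate, such as 50%, that the table hides.* The documents give neither a prevalence nor an improvement rate, so any such figure is only an illustration.

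It is also fair to say that a better denominator does not turn improvement into a treatment effect. The row compares a six-month history with a single last measurement in an uncontrolled arm.

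**Conclusion.** The point holds as a minor one, mainly for the improvement row and for participants without a rating in the phase. As written, the improvement percentage is capped at the pre-treatment prevalence of ideation: 5.1%, 10.2% or 20.3% at an assumed 5%, 10% or 20%. Emergence of serious ideation barely moves, from 1.7% to between 1.8% and 2.1% for two events.

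The conclusion rests on three things: the ordinary reading that the SAF is the divisor, an SAF of about 118, and, for the sizes only, the assumed prevalences. If the shells already restrict the denominator, all that remains is to bring the SAP text into line with them. SAP 5.4.2 plans no hypothesis testing for secondary objectives, and the primary result is unaffected.

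**What to change.** In SAP 2.7.4.3 and the table shell, show n/N (%) for each event and phase. N is the SAF participants with a pre-treatment rating, at least one post-baseline rating in that phase, and the starting state the event requires:

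- improvement: recent-history category 1-5
- emergence of serious ideation: category 0
- worsening to serious ideation: categories 0-3
- any worsening: category below 5
- emergence of behavior: no behavior before treatment

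The counts on the SAF can stay alongside. Requiring a rating in the phase also keeps participants who did not enter the extension out of the extension denominators.

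The cost is a short addition to the SAP and a revised shell; no new data are needed. There are two downsides. Denominators will differ from row to row. The improvement row may rest on very few people, as in the 3-of-6 case, so a footnote should ask the reader to take the count together with the percentage.
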